# **10.4 Exclusion Criteria**

Participants for whom **one of the following** criteria is met will be excluded from trial:

- 1. Circumstances that raise doubt about free, unconstrained consent to study participation (e.g. prisoner or mentally handicapped person)
- 2. Poor general condition where delay in treatment cannot be tolerated or death within four months is likely.
- 3. Poor social condition which would make it unlikely that the patient would be able to complete follow-up
- 4. The patient is pregnant or breast-feeding.
- 5. The patient is infected with HIV with a CD4 count <220 cells/mm^3. If >220 cells/mm^3, patients will be included only if **any** of the following is applicable:
  - The patient is antiretroviral (ARV) naïve and able to postpone commencing HIV treatment for 2 months after the trial has started and then restrict regimens to those containing dolutegravir (see section 12.6.2 on ARVs)

or

The patient is ARV experienced (has been on ARV's a minimum of 5 months) and able to switch to a dolutegravir-based regimen.

- The patient is treated with nucleosidic reverse transcriptase inhibitors (are permitted as concomitant medication).
- The patient is treated with protease inhibitors as part of antiretroviral treatment regimens, which will be stopped at least 3 days before the start of study treatment (WK01, day1) for a patient to be eligible.

- The patient is treated with Efavirenz as part of antiretroviral treatment regimens which would have to be stopped 14 days before the start of study treatment (WK00, Day 01) for a patient to be eligible.
- 6. The patient has a known intolerance to any of the study drugs or concomitant disorders or conditions for which study drugs or standard TB treatment are contraindicated.
- 7. The patient has a history of, or current evidence of clinically relevant cardiovascular metabolic, gastrointestinal, neurological, psychiatric or endocrine diseases, malignancy, or any other condition that will influence treatment response, study adherence or survival in the judgement of the investigator, especially:
  - a. Neuropathy, or significant psychiatric disorder like depression or schizophrenia; especially if treatment for those has ever been required or is anticipated to be required
  - b. Clinically significant evidence of extra-pulmonary TB (e.g. miliary TB, TB meningitis, but not limited lymph node involvement)
  - c. Serious lung conditions other than TB, or significant respiratory impairment in the discretion of the investigator
  - d. Any diabetes mellitus
  - e. Cardiovascular disease such as myocardial infarction, heart failure, coronary heart disease, arrhythmia, tachyarrhythmia, or pulmonary hypertension
  - f. Arterial hypertension (systolic blood pressure ≥140 mmHg and/or diastolic blood pressure of ≥90 mmHg on two occasions during screening).
  - g. Long QT syndrome or family history of long QT syndrome or family history of sudden death of unknown or cardiac-related cause
  - h. Alcohol or other drug abuse that is sufficient to significantly compromise the safety or cooperation of the patient, that includes substances prohibited by the protocol or has led to significant organ damage at the discretion of the investigator.
- 8. Any of the following laboratory findings at screening:
  - a. Serum amino aspartate transferase (AST) and/or alanine aminotransferase (ALT) >3x the upper limit of normal (ULN),
  - b. Serum alkaline phosphatase or y-glutamyl transferase > 2.5x the ULN,
  - c. Serum total bilirubin level >1.5x the ULN
  - d. Estimated creatinine clearance (eCrCl; using the Cockroft and Gault formula [57] lower than 30 ml/min
  - e. Serum albumin < 2.8 g/dl
  - f. Haemoglobin level <7.0 g/dl
  - g. Platelet count <50,000/mm^3,

- h. Serum potassium below the lower level of normal for the laboratory
- i. Blood glucose at screening of less than 70mg/dL (3.9mmol/L)
- 9. ECG findings in the screening ECG: (one or more):
  - a. QTcF of >0.450 s
  - b. Atrioventricular (AV) block with PR interval > 0.20 s,
  - c. QRS complex > 120 milliseconds
  - d. Any other changes in the ECG that are clinically relevant as per discretion of the investigator
- 10. Restricted medication:
  - a. Treatment with any other investigational drug within 1 month prior to enrolment or enrolment into other clinical (intervention) trials during participation.
  - b. Previous anti-TB treatment with drugs active against MTB within the last 3 months prior to screening.
  - c. Unable or unwilling to abide by the requirements regarding restricted medication or have taken restricted medication as described under section 12.6, page 59.
     Restricted medication includes the following drug classes:
    - Anti-TB drugs other than study drugs
    - Medication that lowers the threshold for epileptic seizures
    - Medication that prolongs the QTc interval
    - Drugs that affect monoaminooxidase or serotonin metabolism
    - CYP 450 inhibitors or inducers, including grapefruit containing foods / beverages and St. John's Wort

#### **10.5** Schedule of events

The trial consists of the following periods:

- Screening period: Visit SCR (Day -8 to 0)
- Experimental Treatment Period: Weekly visits from Visit WK00 (Day 01) to WK16 (Day 112 ± 2 days).
- Follow-up period: Visit WK18 (Day 126 ± 4 days), WK26 (Day 182 ± 7 days), WK38 (Day 266 ± 7 days), WK52 (Day 364 ± 7 days)

A tabular overview of the individual timing and details of the respective procedures and laboratory samples to be done at each visit can be found in the Schedule of Events, p.13.

# 10.5.1 Screening Period

Visit SCR (day -8 to 0)		
Administrative & regulatory		Written informed consent
	•	Assign participant screening number
Clinical	• • •	Demographic data: Date of birth, ethnic group, sex Medical history, incl. treatment history and current concomitant medication Physical examination, Vital signs (temperature, blood pressure, pulse, pulse oxymetry and respiratory rate) after 10 mins supine rest Weight (kg)/height (m) Neurological examination, vision testing
Laboratory	Blood • • •	Serum pregnancy test (blood sample of 7.5mL), if female of childbearing potential HIV test and CD4 count (blood sample of 7.5mL) Host biomarker and pharmacogenomics blood sample, if consent for this sub study is given Screening laboratory (blood sample of 12.5mL)
	Urine •	Urine drug screening Urinalysis
Microbiology	•	Spontaneously produced sputum Ziehl-Neelsen smear from concentrated sample Susceptibility testing for RIF and INH by rapid test
Other	•	Inclusion and exclusion criteria Chest X-ray (if no chest X-ray is available no older than 2 weeks) ECG (12 lead, single) after 10 mins supine rest
Study drugs	•	N/A

# 10.5.2 Treatment Period

Visits WK 00 – WK 16 (Day 01 – Day	11	2, each ±2 days with exception of day 14 (-2 days window))
Administrative & regulatory	•	Randomization (before/at WK00 only)

Protocol No: PanACEA - DECODE – 01/ LCB01-0371-20-2-02 Protocol Version No: V2.1, dated 08 September 2021

		
 
Enrolment (WK00 only)
 
Hospitalization* (WK 02 only)
 

Clinical (before intake o	of IMP)	
 
Physical examination, vital signs, weight Additional blood pressure and heart rate measurements at WK00: 1h, 2h and 3h (± 10 mins) after intake of IMP, at WK02 during hospitalization: 1h, 2h, 3h, 4h, 6h (± 10 ins) after intake of IMP with a meal
 
Neurological examination/vision testing (not WK 00)
 
Concomitant medication
 
Adverse events
 
Hospitalization: WK02 visit only, for intensive PK sampling after dosing together with standardized meal.
 

Laboratory Blo (before intake of IMP)	Blood	
 
Safety Lab (WK01-09, WK11, WK13, WK16): haematology and biochemistry (blood sample of 9.5mL), Coagulation only at WK 02 and if clinically indicated (additional blood sample of 3mL); to be sampled before study treatment administration
 
Serum pregnancy test (blood sample of 7.5mL), if female of childbearing potential (WK09 only)
 
Host biomarker blood sampling only at WK02, WK04, WK07, WK11, WK13 and WK16, if consent for this sub study is given
 
Intensive PK sampling DZD (WK02 only): 0 (within 1h before dosing), 1, 2, 4, 8, 12, (± 10 mins) and 24 hours (± 30 mins) after dosing
 

-	Urine	• Urinalysis (WK01-09, WK11, WK13, WK16): per dipstick, additional microscopy on abnormal dipstick results
Microbiology		
 
Sputum (3 samples per visit, one of which may be an early morning sample – to be specified in the microbiology laboratory manual)
 
AFB smear from screening and WK16 samples
 
Culture in BD MGIT liquid media from 2 spot sputum samples
 
Culture on LJ solid media from 2 samples (WK00, WK08, WK12 and WK16 only)
 
Susceptibility testing: minimum inhibitory concentration (MIC) for drugs the participant is receiving will be tested on a representative MTB isolate from baseline and from WK08 or later, if any growth detected
 
Storage of the 3rd sputum sample
 

•	
 
Storage of an isolate obtained at baseline, isolates from treatment visits, and from all cultures positive after WK08 will be stored as specified in the TB Lab Manual
 
Analysis by MBLA and/or sputum LAM, if capacity/budget permits
 

Other	
 
ECG (12-lead, triplicate at WK00, single at WK01-WK09, WK11, WK13, WK16): pre-dose, after 10 minutes lying down, before any other assessment.
 
If a QTcF of >480ms, or a QTc-prolongation over baseline of >50ms is seen in a single ECG during experimental treatment, two more ECGs should be registered, to obtain a more precise, average QTcF measurement.
 

Study drugs	
 
drug dispensing of weekly supply as specified in the Drug Management Plan (DMP)
 
intake of the morning dose of study drug
 
drug accountability (except for Wk00)
 
Compliance assessment
 

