- G) Detailed neurological examination: to include central and peripheral system testing (i.e. cranial nerves testing, vibration sensitivity, position, pin prick, light touch) and vision testing (Snellen, Ishihara). During follow up visits FU 2-4 symptom orientated neurological examination only or to follow up on (S)AEs.
- H) ECG: to be recorded after 10 minutes supine rest, before intake of study treatment. Triplicate ECG at WK00, single ECGs at SCR, WK01 09, WK11, WK13 and WK16. If a QTcF of >480ms, or a QTc-prolongation over baseline of >50ms is seen in a single ECG during experimental treatment, two more ECGs should be registered, to obtain a more precise, average QTcF measurement.
- 1) Microbiology/Susceptibility Testing: rapid test for RIF and INH susceptibility at SCR. Minimum inhibitory concentration (MIC) for study drugs at baseline, and from a representative isolate if any growth at or after WK08.
- J) Screening/Safety lab: full blood count (blood samples of 2mL), ALT, AST, gamma-glutamyl transferase (yGT), Alkaline Phosphatase (AP), Lipase, direct and total bilirubin, albumin, serum creatinine, electrolytes (Na+, K+, Serum Calcium, Magnesium, Cl-, PO4), random glucose (blood samples of 7.5mL for blood chemistry). Urinalysis including dipstick for pH, protein, glucose, ketones, urobilinogen, blood and leukocytes. Urine microscopy on abnormal dipstick results as per the investigator's decision. At SCR and WK02 (and at additional visits, if clinically indicated): Coagulation aPTT, PT, INR (blood samples of 3mL)
- K) Intensive PK sampling (WK02): In all participants, blood samples of 8ml will be taken for measurements of DZD and other study drugs' concentrations over time. Study drugs will be dosed with food. Time of intake of food, drugs and of blood sampling will be recorded. Participants will be hospitalized and receive standard meals at days of intensive PK sampling. Intensive PK time points (7 samples in total) at WK02: 0 (within 1h before dosing), 1, 2, 4, 8, 12, (± 10 mins) and 24 hours (± 30 mins) after dosing

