### 7 NON-IMP DRUGS USED IN THE STUDY

For clarity, all licenced drugs in this study (all drugs other than DZD), are referred to as 'non-IMP study drugs'. BDQ, DLM and MXF are meant by this term. When reference is made to 'study drugs' all drugs including DZD are meant.

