#### 9.2.4 Mycobacteriology Identification and Characterization Endpoint

Sputum cultures from various timepoints during the study will be assessed as follows:

- Minimum inhibitory concentrations (MIC) of BDQ, DLM, MXF, DZD of the infecting strain, at baseline and on representative isolate(s) grown at or after WK08, if any.
- Frequency of acquired mutations in the infecting strain over treatment by whole genome sequencing
- Comparison between bacterial strain causing recurrent disease, and the strain at baseline by whole genome sequencing, to discriminate relapse from re-infection.

These assessments will be performed dependent on availability of lab capacity and budget, so may not be completed for all possible timepoints.

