# **12 STUDY TREATMENT**

# **12.1** Study drug regimens

The study will recruit into the following arms:

Arm 1 (D 0 ): BDM	(bedaquiline, delamanid, moxifloxacin)
Arm 2 (D 400 ): BDM + DZD	(bedaquiline, delamanid, moxifloxacin, delpazolid 400 mg OD)
Arm 3 (D 800 ): BDM + DZD	(bedaquiline, delamanid, moxifloxacin, delpazolid 800 mg OD)
Arm 4 (D 1200 ): BDM + DZD	(bedaquiline, delamanid, moxifloxacin, delpazolid 1200 mg OD)
Arm 5 (D 800-BD ): BDM + DZD	(bedaquiline, delamanid, moxifloxacin, delpazolid 800 mg BID)

BDQ, DLM, MXF are approved drugs. Product Information Leaflets for these drugs will be provided to investigators.

DZD is not an approved drug. It will be manufactured and tested according to Good Manufacturing Practice (GMP) requirements. The Sponsor will provide Ethical Review Boards and site investigators with a set of documents, as required by the local regulatory authority, that provides information on the manufacture and quality control of the raw substance and the medicinal product; Certificates of Analysis (CoA) of the batches to be used; and an Investigational Brochure (IB) that summarizes preclinical and clinical data with respect to DZD.

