# 12.2 Study drug dosage and administration

The experimental and control treatment as described above will be administered daily for 16 weeks (see Table 1. Daily Dosing of Study Medication), together with food.

- Bedaquiline: will be dosed as per the licensed dose: 400 mg orally once daily for the first 14 days, then 200 mg three times a week.
- Delamanid: will be dosed as per the licensed dose: 200 mg orally in two daily doses of 100 mg.
- Moxifloxacin: will be dosed as per the licensed dose: 400 mg orally once daily
- Delpazolid not licensed:
  - Dose: will be according to randomization to dosing arm:
    - Arm 1: 15 participants will receive 0 mg of DZD
    - Arm 2: 15 participants will receive 400 mg DZD orally once daily
    - Arm 3: 15 participants will receive 800 mg DZD orally once daily
    - Arm 4: 15 participants will receive 1200 mg DZD orally once daily
    - Arm 5: 15 participants will receive 800 mg DZD orally twice daily

The daily dose of study drug for participants will be dependent on the subjects' experimental arm as shown in the following table:

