12.3. Development of drug resistance

Any changes in drug resistance profile from baseline will be listed including baseline and any follow-up drug resistance data, culture results, and treatment arm.

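### Protocol 10.5.2 limits MIC testing to each participant's own regimen, which leaves delpazolid out for Arm 1, while the MIC endpoint and schedule footnote call for all four drugs in every arm

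*Protocol*

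**What the plan says.** The operational instruction is in the microbiology row of Protocol 10.5.2: "minimum inhibitory concentration (MIC) for drugs the participant is receiving will be tested on a representative MTB isolate from baseline", with a second test on a week 8 or later isolate if anything grows.

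The Arm 1 regimen in Protocol 12.1 is "bedaquiline, delamanid, moxifloxacin", and Protocol 12.2 confirms it: "Arm 1: 15 participants will receive 0 mg of DZD".

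The endpoint in Protocol 9.2.4 is wider: "Minimum inhibitory concentrations (MIC) of BDQ, DLM, MXF, DZD of the infecting strain, at baseline and on representative isolate(s) grown at or after WK08". SAP 5.4 repeats it. The matching objectives (Synopsis, Protocol 8.1.3, SAP 3.4) name the same four drugs. None of these is limited by arm.

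The susceptibility-testing footnote to the Schedule of Events (Protocol 2) asks for "Minimum inhibitory concentration (MIC) for study drugs at baseline" and on a later isolate if there is growth. Protocol 7 settles what that term covers: "When reference is made to 'study drugs' all drugs including DZD are meant".

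On analysis, SAP 12.3 states: "Any changes in drug resistance profile from baseline will be listed including baseline and any follow-up drug resistance data, culture results, and treatment arm". Table 2.11 then has one column per arm, a row for the drug name, and one row for the proportion developing resistance among participants who did not convert. Neither place names the drugs that count towards that proportion.

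**The concern.** A laboratory or site working from the visit table would request three MICs for Arm 1 and four for every other arm. One working from the schedule footnote or the endpoint would request four for all. These cannot both be carried out.

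Three things are at stake if the narrower text is followed:

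- The stated MIC endpoint is incomplete for DZD in one whole arm, including its baseline distribution.
- Arm 1 is the only group not exposed to DZD. Without its DZD MICs, a rise in Arms 2-5 between baseline and a late isolate has no concurrent reference for how far the assay moves by itself.
- A pooled resistance proportion built on MIC would have one more test that can turn positive in the DZD arms than in the control arm.

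**Working it through.** The plan states no number of MIC results, so there is no figure to reproduce. The check is a comparison of texts, a count, and an illustration.

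**1. Panel by arm under each text**

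| Source | Arm 1 | Arms 2-5 |
|---|---|---|
| Protocol 10.5.2 visit table | 3 drugs | 4 drugs |
| Schedule of Events footnote, read with Protocol 7 | 4 drugs | 4 drugs |
| Protocol 9.2.4 and SAP 5.4 endpoint | 4 drugs | 4 drugs |

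Protocol 13.6 also refers to MICs for the treatment allocated, but its subject is when and where the tests are done. It does not settle the panel.

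**2. Planned baseline results.** Inputs: five arms of 15, 75 in total (Protocol 10.2).

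- Endpoint and footnote: 75 × 4 = 300.
- Visit table: 15 × 3 + 60 × 4 = 45 + 240 = 285.
- Difference: 300 − 285 = 15, all of them DZD MICs in Arm 1. As a share of participants, 15/75 = 20%.

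**3. Effect of panel size on a pooled proportion.** Suppose each drug test has the same independent chance q of a spurious shift between baseline and a late isolate. The documents give no such rate, so q is an assumption, shown over a range. With k drugs tested, P(at least one shift) = 1 − (1 − q)^k.

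| q (assumed) | k = 3 | k = 4 | Gap (points) |
|---|---|---|---|
| 1% | 2.97% | 3.94% | 0.97 |
| 2% | 5.88% | 7.76% | 1.88 |
| 5% | 14.26% | 18.55% | 4.29 |
| 10% | 27.10% | 34.39% | 7.29 |

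The expected number of spurious shifts per tested participant is kq. Testing three drugs instead of four therefore leaves out q/(4q) = 25% of them, whatever q is.

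The table concerns assay movement only. Acquired DZD resistance in Arm 1 may be near zero, since nobody there receives the drug. The percentages also apply only to participants who have a late isolate. That number is unknown and is at most 15 in Arm 1.

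**The case against.** The strongest reply is that this is loose wording in one table cell. That cell does not say the listed drugs are the only ones tested. The four-drug scope appears repeatedly in the objectives, the endpoints and the schedule footnote, and the SAP (February 2023) repeats it after protocol V2.1 (September 2021). The Laboratory Manual, which is not among the documents, may already fix the panel. Protocol 11.2 has the pre-treatment isolate and every positive isolate from week 8 onwards stored for MIC work, so a missing Arm 1 result can be recovered. All of this stands, and it makes the issue an unresolved contradiction and not a settled omission. A reader might infer that Arm 1 will never be tested against DZD; that follows only if 10.5.2 governs.

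A reader might also infer that the comparison of resistance between arms is invalid. The documents do not support that. SAP 12.3 plans a listing and no between-arm test. Results for bedaquiline, delamanid and moxifloxacin remain comparable drug by drug. Whole genome sequencing for acquired mutations is not limited by arm. Only the pooled row of Table 2.11 is exposed, and only if it is based on MIC, which neither document states.

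A third tempting inference is that a three-drug request would unblind the laboratory. Protocol 13.6 defers MICs for the allocated treatment until all other assessments in that laboratory are complete, or moves them to another laboratory. That largely protects the staff who read the cultures. What remains is that the person running the MIC could recognise Arm 1.

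Nor can it be said that assay drift would be inseparable from selection under DZD. Arms 2-5 span 400 to 1,600 mg daily, stored pairs can be retested together, and sequencing is a separate check. The unexposed reference would help, but it is not the only safeguard.

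Finally, Protocol 9.2.4 and SAP 5.4 make these assessments dependent on laboratory capacity and budget. The reason they give is that some timepoints may be incomplete; they do not provide for leaving one drug out of one arm.

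**Conclusion.** The contradiction is real and should be resolved, although its reach is limited. Protocol 10.5.2 implies three drugs for Arm 1; the objectives, the endpoints and the Schedule of Events footnote imply four; nothing ranks them.

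The firm size, conditional on 10.5.2 being followed, is 15 missing baseline DZD MICs, plus the DZD MIC on any late Arm 1 isolate and with it the unexposed reference for DZD MIC change. The bias in the pooled proportion, about 1 to 7 points for assumed per-drug rates of 1% to 10%, is an illustration only. It requires independent and equal rates, an MIC-based definition of resistance, and participants with late growth.

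The primary analysis is not shown to be touched: SAP 10.2 and 10.3 do not name MIC as a predictor in the TTP model.

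**What to change.** 1. In Protocol 10.5.2, replace the words that tie the panel to the participant's own regimen with: for BDQ, DLM, MXF and DZD in all participants regardless of arm. This brings the visit table into line with the schedule footnote, Protocol 9.2.4 and SAP 5.4. A single panel request also no longer reveals the arm.
2. In Protocol 13.6, align the MIC sentence so that it governs only the timing and place of testing, with the same panel for every arm.
3. In SAP 12.3 and Table 2.11, name the drugs that count towards the resistance proportion, use the same panel in every arm, and show DZD separately.
4. Check that the Laboratory Manual carries the same panel.

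The cost is a one-line protocol correction with matching edits, and about 15 baseline DZD MICs plus any late Arm 1 isolates. These can be run on stored isolates and are already within the stated endpoint, subject to its laboratory capacity and budget condition.

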#### 10.5.3 Follow-up Period

#### Visits FU 1 at WK18 (Day 126 ±4 days): all patients

FU 2,3 at WK26, WK38 (Day 182, Day 266, each ±7 days): only patients with sputum culture conversion who end treatment after week 16.

#### FU 4 at WK52: all patients (Day 364 ± 7 days): all patients

All reasonable efforts should be made to achieve on-site visits being conducted. Should this not be possible, a home visit by a study team shall be performed, or, if this is again not possible, telephonic visits will be conducted to obtain health status, information on TB treatment outcome and eventual re-treatment, and pregnancy status if the patient is a woman of childbearing potential.

Administrative & regulatory		• N/A
Clinical		
 
Physical examination, vital signs at FU 1 (WK18); at FU 2-4 (WK26, WK38, WK52) symptom orientated physical examination only or to follow up on (S)AEs
 
Neurological examination/vision testing at FU 1 (WK18); at FU 2-4 (WK26, WK38, WK52) symptom orientated neurological examination only or to follow up on (S)AEs
 
Concomitant medication
 
Adverse events
 

Laboratory	Blood	
 
Safety laboratory (blood sample of 9.5mL) at FU 1 (WK18)
 
Serum pregnancy test (blood sample of 7.5mL), if female of childbearing potential at FU 1 (WK18) only
 

	Urine	Urinalysis at FU 1 (WK18) only
Microbiology		
 
Spot sputum (2 sample)
 
Ziehl-Neelsen smear from concentrated sample
 
Culture in BD MGIT liquid media
 
Culture on LJ solid media
 
Analysis by MBLA and/or sputum LAM, if capacity/budget permits
 

Study drugs		• Standard of care TB treatment from government health system outside of the study, if patient did not meet the definition for sustained culture conversion by week 08.

Protocol No: PanACEA - DECODE – 01/ LCB01-0371-20-2-02 Protocol Version No: V2.1, dated 08 September 2021

